At many centers, a fenestration is created at the time of the Fontan operation to allow a 'pop-off' of systemic venous blood to the pulmonary venous atrium to maintain low Fontan pressures and cardiac output. While this comes at the expense of hypoxemia, in the immediate post-operative period where a transient increase in pulmonary vascular resistance is seen, it yields a shorter duration of chest tube drainage, length of stay, and smoother post-operative course. At Lucile Packard Children's Hospital (LPCH), our surgeons perform the Fontan operation without cardiopulmonary bypass and without a fenestration, citing the hypoxemia, risk of thromboembolism and need for an additional, subsequent, procedure to close the fenestration as their rationale for this approach.

Patients undergoing a Fontan procedure at LPCH have a median length of hospital stay of ~16 days (McCammond et al, Pediatr Cardiol 2012). Nationally, the median length of stay in the largest series is closer to 8 days (Rogers et al, JACC 2012). We believe that the transient elevation in pulmonary vascular resistance resulting from the surgical insult, greater amount of dissection required (our procedures are done without cardiopulmonary bypass), and lack of a fenestration lead to longer duration of chest tube drainage and length of stay seen in our patients. The use of a fenestration in other institutions allows maintenance of cardiac output during this period of limited pulmonary blood flow and reduces Fontan pressures to limit pleural drainage, but does not reduce pulmonary vascular resistance.

Objectives/Purpose

We hypothesize that perioperative use of subcutaneous treprostinil will minimize the surgically-induced elevation in pulmonary vascular resistance, improve postoperative hemodynamics, decrease the need for post-operative fluid resuscitation, and ultimately result in decreased duration of chest tube drainage and shorter hospital length of stay.

In addition, we believe those shown to be particularly responsive to the postoperative treprostinil may be identifiable pre-operatively using vasodilator testing during their routine pre-operative cardiac catheterization.

Study Design

Randomized, blinded, placebo controlled study in which patients undergoing the Fontan operation at LPCH who are enrolled in the study will receive treprostinil (or saline) in the perioperative period. Subcutaneous treprostinil is normally diluted in normal saline. The placebo group will receive saline alone. Patients will be randomized 1:1 (treprostinil : placebo).

Selection and Exclusion of Subjects

All pediatric patients will be considered eligible if they are undergoing a primary Fontan operation and/or pre-Fontan cardiac catheterization at LPCH.

Exclusion criteria:

1. Platelet count < 50K
2. Dermatologic condition that renders the patient unable to tolerate a subcutaneous infusion (can still take part in inhaled vasodilator testing during cardiac catheterization)
3. Currently receiving any vasodilator therapy specifically for the purpose of pulmonary vasodilation (e.g. Phosphodiesterase Type 5 inhibitor, Endothelin receptor antagonist, Prostacyclin)

Treatment of Subjects

The study will be comprised of 2 parts:

1. *Acute, vasodilator testing with inhaled treprostinil (in the catheterization lab) at the time of pre-operative Fontan catheterization*

The protocol for administration of inhaled treprostinil has been previously published (Takatsuki et al, Pediatrc Cardiol 2013) and involves 3-6 breaths (18-36 µg) initially, repeated 5 minutes later if no effect with 9 breaths (54 µg) total. Repeat hemodynamics will be performed after drug administration to measure Fontan/pulmonary artery pressure, pulmonary vascular resistance and cardiac index.

2. *Perioperative infusion of subcutaneous treprostinil surgical Day 0 to Day 7.*

Based on our experience with treprostinil in patients with pulmonary

arterial hypertension ([name] et al, JHLT 2013) and single ventricle physiology, we propose the following protocol for subcutaneous treprostinil administration in the perioperative period:

The subcutaneous catheter will be placed in the operating room (to minimize discomfort) and the initial infusion (either 2 ng/kg/min or saline-only placebo) will be started after anesthetic induction. Treprostinil will be increased by 2 ng/kg/min every 3 hours to a target dose of 10 ng/kg/min within 24 hours. We anticipate the patient will be on 4ng/kg/min at the completion of the Fontan procedure when transferred to the cardiac intensive care unit. The dose will remain at 10 ng/kg/min through day five, though may be decreased if significant hypotension occurs. Beginning on postoperative day six, the dose will be decreased by 2 ng/kg/min every 8 hours with plans for treprostinil to be discontinued by postoperative day seven.

Assessment of Efficacy

The primary outcome is chest tube duration (days). Chest tube removal (the usual determinant of length of stay) is performed, per protocol, when the total output is less than 2 ml/kg/24 hours. Secondary outcomes include hospital length of stay (days), total volume of chest tube output, time to extubation, amount of fluid intake per 24 hours, blood product administration per 24 hours, urine output per 24 hours, markers of cardiac output (lactate, mixed venous saturation, chemistry panel

looking at end organ function such as BUN, creatinine, liver function tests), in hospital mortality and 12 month mortality. Hemodynamics will include Fontan and atrial pressures while indwelling catheters are present, systolic blood pressure and heart rate over the first 96 hours post-operative. All data collected are part of standard care for this population in our institution.

Cardiac catheterization derived pre-operative hemodynamics, and response to inhaled treprostinil will be recorded and compared to post-operative hemodynamics and post-operative course to determine whether post-operative response to subcutaneous treprostinil correlates with pre-operative testing and to determine whether pre-operative hemodynamics and response to treprostinil “testing” in the catheterization lab can predict which patients received the most benefit from treprostinil.

Assessment of Safety/Adverse Events and report

A research coordinator will track adverse events, which will be immediately reported to Drs. [name] and [name]. The research staff, led by [name], will be responsible for reporting these events to the IRB. A DSMB will meet after the initial six patients are enrolled and quarterly thereafter.

An adverse event is any untoward medical experience occurring to a subject during a clinical trial whether or not it is related to the study drug. An adverse event may include an intercurrent illness, injury, or any other concomitant impairment of the subject’s health, as well as abnormal laboratory findings if deemed to have clinical significance. Adverse events may also include worsening of

an existing symptom or condition or post-treatment events that occur as a result of protocol-mandated procedures.

A serious adverse event (SAE) is an adverse event occurring at any dose that results in any of the following outcomes:

- Death
- A life-threatening adverse event
- Inpatient hospitalization or prolongation of existing hospitalization
- A persistent or significant disability/incapacity
- A congenital anomaly/birth defect

In addition, important medical events that may not result in death, be life-threatening, or require hospitalization may be considered serious when, based upon appropriate medical judgment, they may jeopardize the subject and require medical/surgical intervention to prevent one of the outcomes listed above. Life-threatening means that the subject was, in the view of the investigator, at immediate risk of death from the event as it occurred. It does not mean that the event, had it occurred in a more severe form, might have caused death.

An adverse event or SAE occurring during the study must be documented in the subject's source documents and on the appropriate CRF page. Information relating to the adverse event such as onset and cessation date and times, intensity, seriousness, relationship to study drug, and outcome is also to be documented in the CRF. Where possible, adverse events should be recorded using standard medical terminology. If several signs or symptoms are clearly related to a medically defined

diagnosis or syndrome, the diagnosis or syndrome should be recorded on the CRF page, not the individual signs and symptoms.

All adverse events should be followed until either resolution (or return to normal or baseline values), until they are judged by the investigator to no longer be clinically significant, or for at least 4 weeks if the adverse event extends beyond the final visit. All SAEs that occur during the study will be followed until resolution, death, or the subject is lost to follow-up even if they are ongoing more than 4 weeks after completion of the final visit. Supplemental measurements and/or evaluations may be necessary to investigate fully the nature and/or causality of an adverse event or SAE. This may include additional laboratory tests, diagnostic procedures, or consultation with other healthcare professionals. CRF pages should be updated with any new or additional information as appropriate.

The investigators shall report all serious adverse events in English to UT GDS by fax (+ 1 [contact]/ [name]) (US/ex-US) or e-mail ([contact]) using a MedWatch 3500A Form/CIOMS I Form (US/ex-US). Cases requiring expedited reporting to the regulatory authority should be sent to UT GDS on or before the date Investigator send the report to the authority and should be the exact document Investigator is submitting to the regulatory authority. All other serious cases should be submitted within 10 days of Investigator initial awareness. For purposes of reportability, UT GDS Day 0 will be the date when we receive the case report from Investigator.

The investigators further agrees to make available promptly to UT GDS such records (e.g., source documents) as may be necessary and pertinent for UT GDS to further investigate a case report.

Should the Investigator receive follow-up information for any serious adverse event reports, Investigator shall be responsible for reporting all follow up to UT GDS by fax (+ 1 [contact]/ [name]) (US/ex-US) or e-mail ([contact]) using a MedWatch 3500A Form/CIOMS I Form/MedWatch 3500A Form (US/ex-US), based upon the timelines above, and should be the exact document the Investigator is submitting to the regulatory authority;

In accordance with FDA, European, and national regulations, the sponsor will notify the FDA, other competent authorities, and all participating investigators of any adverse event that is considered to be possibly attributable to study drug and is both serious and unexpected. The investigator must report these adverse events to their IRB or EC in accordance with applicable national regulations and guidelines set forth by the IRB or EC.

Study Discontinuation

The study will end when 42 patients (21 each in the treprostinil and placebo group) have been enrolled. All patients will be under the direct care of physicians in the Division of Pediatric Cardiology throughout the treatment portion of the protocol (in the cardiac catheterization lab, the cardiac intensive care unit, and

acute care floor). Phone follow up with their primary cardiologist and family will be collected 12 months post-operatively.

Statistics, including power calculations and details of data analysis plan

Chest tube duration (days) was analyzed on the natural logarithm scale. The geometric mean of chest tube days in the historical cohort of 138 patients (unselected, date of operation 2004-2012) was 11.8 days and the standard deviation (log scale) was 0.52. With 42 subjects randomized 1:1 we have 80% power to detect a 33% reduction in CT days. These calculations are based on the use of a two-sample t-test with sample sizes 42 and 138 and a one-sided significance level of 5%.

Data handling and record keeping

All data will be kept in RedCap in a dedicated, HIPAA compliant, database. The patient will be coded by as 001 - 042 based on date of enrollment. Only the research staff will have access to the database and all exported data for analysis will be free of identifying information. Data will be entered on a Stanford secured, encrypted, password protected computer.

References

Fontan F, Baudet E: Surgical repair of tricuspid atresia, Thorax. 1971

May;26(3):240-8.

Jacobs JP, Maruszewski B: Functionally univentricular heart and the Fontan operation: lessons learned about patterns of practice and outcomes from the congenital heart surgery databases of the European association for cardio-thoracic surgery and the society of thoracic surgeons. World J Pediatr Congenit Heart Surg. 2013 Oct;4(4):349-55.

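### Must the plan say how chest tube duration is valued when a child dies with a tube in place or has a tube reinserted?

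*Combined protocol and SAP*

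**What the plan says.** The Assessment of Efficacy section names the outcome, "The primary outcome is chest tube duration (days"), and adds that removal "is performed, per protocol, when the total output is less than 2 ml/kg/24 hours". Death appears in the same section only as separate secondary outcomes: "in hospital mortality and 12 month mortality".

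The statistics section says "Chest tube duration (days) was analyzed on the natural logarithm scale". It gives a historical geometric mean of 11.8 days and a log-scale standard deviation of 0.52, and claims 80% power for a 33% reduction. The only test named is in the power statement: "These calculations are based on the use of a two-sample t-test with sample sizes 42 and 138 and a one-sided significance level of 5"%. The Study Design section says "Patients will be randomized 1:1 (treprostinil : placebo"), and Study Discontinuation says "The study will end when 42 patients (21 each in the treprostinil and placebo group) have been enrolled".

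No section gives a value for a child who dies before tube removal, says whether first or final removal ends the count, or sets out a rule for missing data or censoring.

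**The concern.** For a child who dies with a tube in place, the removal threshold is never met and the duration is undefined. At least three codings fit the text: count days to death, leave the child out, or assign the longest duration seen in either arm. The first is uncomfortable, because an early death then counts as a short, favourable duration. Reinsertion raises a similar question, since the count could end at first or at final removal.

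With 21 per arm, each child carries about 5% of an arm's mean (1/21), so one coding decision can move the estimate and the p-value. If the decision were made once the arms were known, the analyst could take the version that favours the drug, and the one-sided error would exceed 5%.

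**Working it through.** **Inputs from the documents.** 21 per arm; control geometric mean 11.8 days; log SD 0.52; ratio 0.67, so a log difference of ln(0.67) = -0.4005; one-sided 5%. The day and arm of death, the risk of death and the reinsertion rate are assumptions, because the documents give none.

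**The plan's own figure.** SE = 0.52 × √(2/21) = 0.1605, and 0.4005/0.1605 = 2.496. Normal power is Φ(2.496 - 1.645) = 80.3%; the exact t-test gives 79.0%. Both agree with the stated 80%, so 21 v 21 is used below. The printed sizes of 42 and 138 would give 99.7%; that discrepancy is a separate matter.

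**Shift from one death.** A typical treated child has 11.8 × 0.67 = 7.9 days. Coding that child as v days moves the log difference by [ln(v) - ln(7.9)]/21:
- v = 2: (0.693 - 2.068)/21 = -0.065, so the ratio goes from 0.67 to 0.63.
- v = 10: (2.303 - 2.068)/21 = +0.011, ratio 0.68.
- v = 30: (3.401 - 2.068)/21 = +0.064, ratio 0.71.

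**Power at the planned effect, one death** (simulated trials, t-test on log days; 79% with no death):

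| Death | Days to death | Excluded | Longest observed | Any of the three disagree | First two disagree |
|---|---|---|---|---|---|
| Treprostinil, day 2 | 86% | 78% | 61% | 25% | 8.1% |
| Treprostinil, day 10 | 78% | 78% | 61% | 17% | 0.7% |
| Placebo, day 2 | 54% | 78% | 85% | 31–32% | 24.6% |
| Placebo, day 10 | 79% | 78% | 85% | 7% | 0.6% |

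The three codings therefore agree on significance in 68% to 93% of trials. For a day-10 death, days to death and exclusion almost always agree.

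**Error with no drug effect, death at day 2.** If the drug affects neither death nor duration, the death is equally likely in either arm:
- Days to death: (9.4 + 0.7)/2 = 5.05%.
- Exclusion: (5.0 + 5.0)/2 = 5.0%.
- Longest observed: (1.8 + 8.1)/2 = 4.95%.

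Each coding, fixed in advance, holds the level. Taking the most favourable of the three after unblinding gives on average 8.7%, 7.9% and 6.8% for a death at day 2, 5 and 10.

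**Allowing for the chance that no death occurs.** With a risk of 1%, 2% or 3% per child and death uniform over days 1 to 10, the chance of at least one death is 1 - 0.99^42 = 34%, 1 - 0.98^42 = 57% and 1 - 0.97^42 = 72%. Choosing the best of three codings then rejects in 6.0%, 6.9% and 7.5% of trials. If the choice is only between days to death and exclusion, the figure stays at about 6.1% or less.

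**Reinsertion.** If 10% of children have 7 more tube days, power is 79% counting to first removal and 74% counting to final removal. The two results disagree in 9.7% of trials, and taking the better one rejects 6.4% under no effect. Either count, fixed in advance, holds 5%.

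**Is one coding better?** Average power over arms for a day-2 death is (86 + 54)/2 = 70% for days to death, 78% for exclusion and (61 + 85)/2 = 73% for longest observed. Exclusion keeps the most power but drops a randomized child because of a post-randomization event. Longest observed keeps every child and counts death as a bad outcome, but moves the expected ratio from 0.67 to about 0.72 or 0.64, depending on the arm.

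**The case for a change.** The strongest case for a change is that the plan foresees death by listing it as an outcome, that tubes stay in for much of the admission (geometric mean 11.8 days against a median stay of about 16), and that a few sentences would close the gap. In a trial of 42 with one primary outcome, a decision about one child should not be open once the arms are known. A treprostinil death at day 2 coded as two tube days has a 9.4% chance of a false positive under no drug effect, against a nominal 5%.

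Much of this stands. The omission is real, the calculations reproduce, and the rule should be settled before the codes are opened. What does not stand is that the plan is wrong as written:
- The 9.4% applies only if the death falls on treprostinil; the matching figure for a placebo death is 0.7%.
- The inflated error needs an event to occur and a choice made after unblinding. The plan provides for neither, and the trial is blinded.
- The largest disagreements need a very early death, the longest-observed coding, or both, and nothing in the text suggests that coding.
- The cost is not clearly nil. The plan says "All data collected are part of standard care for this population in our institution", but it does not list reinsertion dates or tubes placed at a readmission, so a fuller definition might need data not shown to be collected.

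**Conclusion.** No change to the plan follows. The outcome definition omits a detail, but contains no wrong rule or number. The coding can change the conclusion if a child dies with a tube in place: in about 7% to 32% of trials for one assumed death between day 2 and day 10 across three codings, and in about 0.6% to 25% between days to death and exclusion alone. These figures assume a log-scale t-test of 21 v 21 at the planned effect, and the documents give no event rate from which to judge how likely such a death is.

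Any one rule fixed before unblinding holds 5% on average, and the choice between rules is a fair trade-off between power, keeping every randomized child, and counting death as a bad outcome. Analysts would ordinarily fix the rule while blinded. Because in-hospital mortality is an outcome in its own right, a death would also be visible beside the primary result, whichever coding is used.

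### Mixed venous saturation is listed as a cardiac output marker without a paired arterial saturation or hemoglobin, so an oxygenation difference between arms could mimic or mask an output effect

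*Combined protocol and SAP*

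**What the plan says.** All references are to the combined protocol and SAP.

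- **Output markers.** Assessment of Efficacy gives the secondary outcomes as including "markers of cardiac output (lactate, mixed venous saturation, chemistry panel", and the sentence continues "looking at end organ function such as BUN, creatinine, liver function tests), in hospital mortality and 12 month mortality". Mixed venous saturation is thus one of several markers.
- **Post-operative hemodynamics.** The same section states: "Hemodynamics will include Fontan and atrial pressures while indwelling catheters are present, systolic blood pressure and heart rate over the first 96 hours post-operative". Arterial saturation and measured cardiac output are not in that list.
- **Hemoglobin.** It is not listed anywhere as study data. Transfusion is, as "blood product administration per 24 hours".
- **Measured output.** Treatment of Subjects plans repeat readings at the pre-operative inhaled test to "measure Fontan/pulmonary artery pressure, pulmonary vascular resistance and cardiac index". No such measurement is planned after surgery.
- **Data source.** "All data collected are part of standard care for this population in our institution".
- **Analysis.** No section describes how mixed venous saturation will be analyzed or interpreted.

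**The concern.** Output is inversely related to the gap between arterial and mixed venous saturation, not to the venous value by itself. With only the venous value, a change in oxygenation cannot be told apart from a change in flow.

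Randomization does not remove this. It balances the arms at baseline, but an oxygenation difference that arises after randomization as a consequence of treatment is part of the arm comparison. The protocol's own outcomes suggest how that could happen. Time to extubation is a secondary outcome, so ventilatory support could differ by arm at a given hour. Blood products are also an outcome, and hemoglobin moves mixed venous saturation too.

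What is at stake is the reading of one secondary marker. Of the post-operative markers listed, it is the one tied most directly to output, because lactate and the chemistry panel are indirect and do not separate oxygenation from flow.

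**Working it through.** The plan gives no figure for mixed venous saturation, so there is none to reproduce. Its only power figure, in the Statistics section, concerns chest tube duration and does not enter here.

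**Formula.** With dissolved oxygen ignored, the Fick relation is

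SvO2 = SaO2 - E, where E = 100 × VO2 / (CI × Hb × 13.6)

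SvO2 is mixed venous saturation, SaO2 arterial saturation, E extraction in saturation points, VO2 oxygen consumption, CI cardiac index and Hb hemoglobin. If VO2, CI and Hb are fixed, E is constant and the slope of SvO2 on SaO2 is exactly 1.

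**Inputs.** The documents give none of these values, so all are assumptions. The base case is VO2 160 mL/min/m2, CI 3.0 L/min/m2 and Hb 13 g/dL: E = 16000 / (3.0 × 13 × 13.6) = 30.2 points. Rounded, that is arterial 95%, venous 65%, E = 30.

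**Size of a real effect.** A 10% rise in output gives SvO2 = 95 - 30/1.10 = 67.7, a rise of 2.7 points. An arterial fall of 2.7 points would hide it.

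**Size of a spurious effect.** If SaO2 shifts by d at unchanged output and SvO2 is read as though SaO2 had stayed put, the apparent output ratio is 30 / (30 - d):

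| Arterial shift d (points) | Ratio | Apparent change in output |
|---|---|---|
| +2 | 30/28 = 1.071 | about +7% |
| +3 | 30/27 = 1.111 | about +11% |
| -2 | 30/32 = 0.938 | about -6% |
| -3 | 30/33 = 0.909 | about -9% |
| -5 | 30/35 = 0.857 | about -14% |

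Rises and falls are not symmetric. A rise of 5 points (30/25, or +20%) is left out of the table because it takes 95% to 100%, the physical ceiling.

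**Range.** The ratio depends on E and not on the arterial level. Over assumed combinations giving E from 22.6 to 60.2 points:

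- +3 points: 22.6/19.6 = 1.153 to 60.2/57.2 = 1.052, or about +15% to +5%.
- -3 points: 22.6/25.6 = 0.883 to 60.2/63.2 = 0.953, or about -12% to -5%.

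**Hemoglobin.** At the base case, changing only Hb from 12 to 14 g/dL moves SvO2 from 62.3 to 67.0, which is 4.7 points and more than the 2.7-point signal. Point-for-point movement with SaO2 is therefore conditional, and the arteriovenous difference also needs hemoglobin beside it.

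**Effect of pairing.** In SaO2 - SvO2 a pure arterial shift cancels exactly. In the extraction ratio it does not: 30/95 = 31.6% against 30/98 = 30.6% after a 3-point arterial rise.

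**The case against.** The strongest reply is that the plan never equates this marker with output. It stands in a list with lactate and a chemistry panel, nothing converts it to a percentage change in flow, and calling it a marker claims little. That stands: the percentages above are a translation to show scale, not a reading the plan makes. But the companion markers cannot show whether a difference in mixed venous saturation came from oxygenation.

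A reader might infer from the listing that mixed venous saturation is the sole output marker. The sentence itself contradicts that; what is missing is a paired arterial value.

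A reader might also infer that treprostinil is known to change oxygenation in this trial, pointing to the remark in the opening background text, "While this comes at the expense of hypoxemia". That remark concerns a fenestration, and the surgeons at this center operate "without a fenestration, citing the hypoxemia, risk of thromboembolism" among their reasons. The documents nowhere say that the drug shifts arterial saturation, and without a fenestration the scope for a shunt-related shift may be smaller.

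It is also fair that the efficacy lists are introduced as inclusive and the case report form is not shown, so arterial saturation and hemoglobin may be available in the chart. Clinically significant abnormal laboratory findings already count as adverse events under Assessment of Safety. Both points lower the cost of the change and the urgency of the safety aspect. Neither commits the trial to a paired reading or a comparison of arterial saturation by arm.

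**Conclusion.** The point holds as a limited one about measurement. The listed post-operative data do not allow the arteriovenous difference to be formed, and an arterial shift of 2 to 3 points between arms would be about as large in mixed venous saturation as a true 10% change in output. This rests on the assumed 95/65 baseline and on fixed oxygen consumption and hemoglobin. Over assumed extraction of 23 to 60 points, a 3-point arterial rise looks like +5% to +15%.

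Whether any such shift will occur, and in which direction, cannot be told from the documents; without arterial values the trial could not tell either. The effect is confined to the interpretation of one secondary marker. Chest tube duration does not depend on it, so the primary outcome, power and sample size are unaffected. This is a cheap improvement, not a flaw that threatens the trial's conclusions.

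**What to change.** In Assessment of Efficacy:

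1. Record arterial saturation and hemoglobin with each mixed venous reading, where available.
2. Report the arteriovenous saturation difference as the saturation-based output marker, with hemoglobin beside it. Prefer the difference to the extraction ratio, which does not fully cancel an arterial shift.
3. Keep raw mixed venous saturation as a supplement, so that no listed outcome is lost.
4. Report arterial saturation by arm, which also gives a direct description of oxygenation on treatment.

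The cost is two extra case report form fields. That both values are routine in this unit is an assumption, though a reasonable one given the statement that all study data come from standard care. Readings without a paired arterial value would contribute only to the raw summary. Variation in oxygen consumption remains a limitation after the change and should be stated as one. Sample size and the primary analysis do not change.

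### The sample sizes written for the power calculation (42 and 138) do not give the stated 80% power and do not describe the randomized comparison; 21 against 21 does

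*Combined protocol and SAP*

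**What the plan says.** The Study Design section describes a randomized, blinded, placebo-controlled trial with 1:1 allocation, and the Study Discontinuation section ends enrollment at 42 patients, 21 per group. Under Assessment of Efficacy the primary outcome is chest tube duration in days.

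The section on statistics, power calculations and data analysis plan contains:

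- the scale: "Chest tube duration (days) was analyzed on the natural logarithm scale";
- a historical cohort of 138 unselected patients, with geometric mean 11.8 days and log-scale standard deviation 0.52;
- the power claim: "With 42 subjects randomized 1:1 we have 80% power to detect a 33% reduction in CT days";
- its basis: "These calculations are based on the use of a two-sample t-test with sample sizes 42 and 138", at a one-sided 5% level.

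No separate sentence names the primary comparison, the primary model, a covariate or a rule for missing values.

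Pre-operative catheterization data are collected, but for another purpose. Assessment of Efficacy says: "Cardiac catheterization derived pre-operative hemodynamics, and response to inhaled treprostinil will be recorded and compared to post-operative hemodynamics and post-operative course". The aim given there is to learn whether they "can predict which patients received the most benefit from treprostinil".

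**The concern.** Two consecutive sentences give different designs for one calculation. The first is the randomized trial of 42 patients split equally. In the second, 42 is the whole trial and 138 is the size of the historical cohort, so the test it describes sets all enrolled patients, treated and placebo together, against earlier patients from the same hospital.

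This matters for two reasons. A reader cannot confirm the power from the sizes given. Also, because the primary comparison is written nowhere else, this sentence is the only place from which an analyst could take it. A test of 42 against 138 would mix treated with untreated patients and give up the protection of randomization, since any change in care since 2004-2012 would fall into the difference.

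**Working it through.** **Inputs, all from the statistics section unless noted.** Log-scale SD 0.52; reduction 33%; one-sided level 5%; 21 per arm (Study Discontinuation); historical cohort 138.

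**Effect on the log scale.** −ln(1 − 0.33) = −ln(0.67) = 0.4005.

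**Formula.** SE = 0.52 × √(1/n₁ + 1/n₂). Noncentrality = 0.4005 / SE. Power is the chance that a noncentral t with n₁ + n₂ − 2 degrees of freedom exceeds the one-sided 5% critical value. The last column solves the same equation for the reduction that gives 80% power.

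| Comparison | SE | Noncentrality | df | Critical t | Power for 33% | Reduction detectable at 80% |
|---|---|---|---|---|---|---|
| 21 v 21 | 0.1605 | 2.496 | 40 | 1.684 | 79.0% | 33.4% |
| 42 v 138 | 0.0916 | 4.370 | 178 | 1.653 | 99.7% | 20.4% |
| 21 v 138 | 0.1218 | 3.288 | 157 | 1.655 | 94.8% | 26.2% |

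The plan's figure is reproduced by 21 against 21: 79.0% with the t distribution, or 80.3% with the normal approximation. Neither calculation involving 138 gives it.

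**What a pooled comparison would estimate.** The 99.7% supposes that all 42 patients have the full reduction. With half on placebo, and placebo patients like the historical ones, the pooled log difference is 0.4005 / 2 = 0.2002, a ratio of exp(−0.2002) = 0.82 rather than 0.67. So 42 against 138 does not target the treatment effect even when history and placebo agree.

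**Optional covariate adjustment, for 21 against 21.** The documents give neither the R-squared of a pre-operative value with log chest tube days nor the share missing; both are assumed below. With complete data, one degree of freedom is lost (39 df) and SE = 0.52 × √(1 − R²) × √[(2/21)(1 + 1/38)], where 1/38 allows for chance imbalance. The rows with missing values come from simulation (1,000,000 trials per setting, normal covariate, values missing at random, missing values replaced by the mean pooled over both arms). Unadjusted power is 79.0%.

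| R-squared | 0 | 0.05 | 0.10 | 0.20 |
|---|---|---|---|---|
| Complete data | 78.1% | 79.9% | 81.8% | 85.6% |
| 25% missing | 78.2% | 79.4% | 80.7% | 83.6% |
| 50% missing | 78.1% | 79.0% | 79.8% | 81.6% |

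With 25% missing, the change is −0.9, +0.4, +1.7 and +4.6 points. Simulated one-sided type I error with imputation stayed at 5.0% to 5.1%. Dropping patients with a missing value instead would cost roughly 3.5 to 13 points over the same R-squared range, because about 16 per arm would remain.

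**The case against.** **On the sizes.** The sentence speaks only of the power calculation, and the rest of the protocol is plainly a randomized placebo-controlled trial. A sensible analyst would compare the two arms on log days by t-test, and the stated 80% is right for that. This stands, and it limits the point. A reader might infer that the sponsor intends a historical-control analysis, or that the trial was sized wrongly. The documents support neither: 1:1 randomization is stated repeatedly, and 21 per arm matches the stated power. What remains is that the written basis is wrong and no other sentence names the primary comparison.

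**On adjustment.** A reader might also infer that leaving out a covariate is an error, or that pulmonary vascular resistance is a known predictor that the plan has overlooked. That does not follow. An unadjusted t-test is valid for a randomized comparison. The introductory background attributes long drainage to the surgically induced rise in resistance, greater dissection and lack of a fenestration, not to the pre-operative value. The planned use of the catheterization data concerns who benefits from treprostinil, which is effect modification rather than prognosis in both arms. Nor do the documents favor resistance over other measures: "Repeat hemodynamics will be performed after drug administration to measure Fontan/pulmonary artery pressure, pulmonary vascular resistance and cardiac index" lists three together, and a pre-drug value is itself inferred from the first word. Up to an R-squared of 0.10 with 25% missing, the change is only about −1 to +2 points, close to the 1.3-point gap between the normal and t calculations. The objection stands in full against presenting adjustment as a correction; it does not exclude it as an option.

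**Conclusion.** The main point holds. The sizes 42 and 138 contradict the 1:1 design in the sentence before them and yield 99.7% power, not 80%. The stated power belongs to 21 against 21. This conclusion rests only on the plan's own SD, effect, level and sample sizes. It is an error in the written basis and leaves the primary comparison unstated; it does not show that the trial has too few patients for its stated one-sided target.

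Covariate adjustment is secondary and of uncertain sign: about −1 to +5 points of one-sided power, on an assumed R-squared of 0 to 0.20 and an assumed 25% missing. With that share missing, it begins to help at an R-squared of about 0.035, and it costs about 1 point if the covariate is not prognostic.

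**What to change.** 1. In the statistics section, replace the sizes 42 and 138 by 21 and 21, and keep the 138 historical patients only as the source of the mean and SD.
2. Add a sentence naming the primary analysis: randomized treprostinil against randomized placebo on log chest tube days, reported as a ratio of geometric means with its confidence interval.
3. Optional, and to be settled before unblinding: name one pre-operative hemodynamic value measured before inhaled treprostinil (pulmonary vascular resistance is one example) as a linear covariate. Replace missing values by the mean pooled over both arms, so that all 42 patients stay in the analysis, and report the unadjusted t-test alongside. The missing-value rule is needed because eligibility covers patients "undergoing a primary Fontan operation and/or pre-Fontan cardiac catheterization at LPCH", so some randomized patients may have no in-center catheterization.

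Items 1 and 2 cost only wording. Item 3 needs no data beyond what is already planned; its price is the missing-value rule and about 1 point of power if the covariate turns out to be uninformative.
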